13.6.2.2. Non-fatal and non-life-threatening SUSARs

All other SUSARs and safety issues must be reported to all parties listed in 12.6.1 as soon as possible but no later than **14 calendar days** after first knowledge of the minimum criteria for expedited reporting. Further relevant follow-up information should be given as soon as possible.

13.6.3. How to report?

13.6.3.1. Minimum criteria for initial expedited reporting of SUSARs

Information on the final description and evaluation of an adverse reaction report may not be available within the required time frames for reporting. For regulatory purposes, initial expedited reports should be submitted within the time limits as soon as the minimum following criteria are met:

- a) a suspected investigational medicinal product
- b) an identifiable participant (e.g. trial participant code number)
- c) an adverse event assessed as serious and unexpected, and for which there is a reasonable suspected causal relationship
- d) an identifiable reporting source

and, when available and applicable:

- an unique clinical trial identification
- an unique case identification (i.e. sponsor's case identification number)

13.6.3.2. Follow-up reports of SUSARs

In case of incomplete information at the time of initial reporting, all the appropriate information for an adequate analysis of causality should be actively sought from the reporter or other available sources. Further available relevant information should be reported as follow-up reports.

In certain cases, it may be appropriate to conduct follow-up of the long-term outcome of a particular reaction.

13.6.3.3. Format of the SUSARs reports

Electronic reporting is the expected method for expedited reporting of SUSARs to the competent authority. The format and content as defined by the competent authority should be adhered to.

14. Toxicity - Emergency Procedures

Development of facial oedema, an extensive urticarial rash or severe stomach cramps within the first 48-hours post-treatment will be considered as a severe adverse reaction, and the child will be referred to the local health centre IV at Kigorobya for care by the trial clinical officer. A follow-up visit from the nursing qualified Trial Site Manager will be conducted once the child has returned home. In the event of facial oedema as a result of treatment the child will be permanently removed from further participation in the trial.

15. Evaluation of Results (Definitions and response/evaluation of outcome measures)

ISRCTN Number: 16994599 Page 31 of 48

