Summary of eligibility criteria	 Inclusion Criteria: Aged 6-14yrs Resident in study village for at least 2years Parental/Guardian consent granted Child assent granted Exclusion Criteria Previous facial oedema after praziquantel treatment Known neurocysticercosis or ocular cysticercosis
Investigational medicinal product and dosage	Praziquantel, ~40mg/kg according to standardised WHO dose pole.
Active comparator product(s)	Standard annual treatment with pra- ziquantel
NIMPs and Challenge Agents	_
Route(s) of administration	Oral
Maximum duration of treat- ment of a participant	One oral dose per treatment round
Procedures: Screening & enrolment	Demographic data - age, sex, length of residency, history of severe praziquantel side effects
Procedures: Baseline	Ultrasonography - WHO Niamey Proto- col Faecal parasite egg counts Urine samples Blood sample
Procedures: Treatment period	Control arm – PZQ treatment annually Intervention arm 1 – treatment with PZQ twice annually Intervention arm 2 – treatment with PZQ 4 times annually
	Treatment schedule based around Ugandan school terms, at approximate but not exactly equal intervals.
	At time of 1-year treatment of all arms: Faecal parasite egg counts on sub-set of children (n =120, split approximately equal across treatment arms) Urine samples

Procedures: End of trial	Ultrasonography - WHO Niamey Protocol Faecal parasite egg counts Blood sample Urine sample Final treatment
Procedures for safety mon- itoring during trial	Treatment observed and managed for AEs for at least one hour after administration. 24-hour post-treatment follow-up of participants by health professional. Treatment side effects recorded. Severe adverse effects reported to [name], VCD-Ministry of Health and [name], University of Cambridge ([name], University of Cambridge, CI maternity cover) for notifications
Criteria for withdrawal of participants	Severe Adverse Event/Reaction Withdrawal of assent/consent

5. Trial Flow Chart

Final outcome measured 2-years post 1^{st} treatment. Intermediate assessments at 1-year post 1^{st} treatment.

Assessment for primary outcomes – Ultrasonography according to WHO Niamey Protocol for Schistosomiasis. Prevalence of periportal fibrosis (protocol scores C, D, E or F) at 2-years.

Assessment for secondary and exploratory outcomes :-

Stool sample collection for parasitology egg counts, pre-annual treatment and around 4-weeks post treatment at baseline and 2-years for treatment efficacy measurement.

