8.4. Participants Trial Duration

Participants will be enrolled prior to the start of any other trial visits/treatments. The active treatment phase will last 2-years. All participants will be enrolled for the duration of the 2-year follow-up post 1st treatment. The time the participants will be enrolled in the trial has been elongated due to COVID-19 restrictions. Please see Diagram 'Chronological Trial Plan' in Section 12.6

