10.5. Participant Withdrawal Criteria

- Severe Adverse Reaction to praziguantel
- Withdrawal of consent/assent

11. Trial Treatments

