11.1.1.8 Known drug reactions

Neurological

Headaches – very common (>10%)

Dizziness - very common (>10%)

Vertigo, drowsiness – common (1-10%)

Seizures – very rare (<0.01%)

Gastro-intestinal

Gastrointestinal and abdominal pains- very common (>10%)

Nausea – very common (>10%)

Vomiting – very common (>10%)

Anorexia – common (1 – 10%)

Diarrhoea – common (1 – 10%)

Bloody diarrhea - - very rare (<0.01%)

Dermatological

Urticaria – very common (>10%)

Cardiovascular

Unspecified arrhythmias – very rare (<0.01%)

Immune system disorders

Allergic reaction – very rare (<0.01%)

Polyserositis – very rare (<0.01%)

Eosinophilia – very rare (<0.01%)

Jarisch-Herxheimer reaction – very rare (<0.01%)

Hepatobiliary disorders

Liver function tests increased - rare (0.01 - 0.1%)

Musculoskeletal and connective tissue disorders

Myalgia – common (1 – 10%)

General disorders

Fatigue-very common (>10%)

Feeling unwell (asthenia, malaise) – common (1 – 10%)

Fever-common (1 - 10%)

Adverse reactions with food, over the counter drugs or commonly prescribed drugs are not reported.

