11.1.1.10. Procedures for monitoring treatment compliance

Treatment will be observed by a member of the study team trained in dispensing praziquantel. If the individual refuses treatment this will be entered into the treatment log.

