13.4.3. Clinical assessment of severity

Mild: The participant is aware of the event or symptom, but the event or symptom is easily tolerated

Moderate: The participant experiences sufficient discomfort to interfere with or reduce his or her usual level of activity

Severe: Significant impairment of functioning; the subject is unable to carry out usual activities and / or the participant's life is at risk from the event.

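### Section 14 and the withdrawal criteria can take a child out of the trial, not only off praziquantel, and so discard a 2-year outcome that could still be collected safely

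*Protocol*

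**What the plan says.** Three places in the protocol deal with withdrawal after a severe event.

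- **Section 14 (Toxicity – Emergency Procedures).** It names three reactions. Facial oedema, "an extensive urticarial rash or severe stomach cramps within the first 48-hours post-treatment will be considered as a severe adverse reaction". All three lead to referral to the health centre and a later follow-up visit. For one of them it adds: "In the event of facial oedema as a result of treatment the child will be permanently removed from further participation in the trial".
- **Section 10.5 (Participant Withdrawal Criteria).** It has two entries: "Severe Adverse Reaction to praziguantel" (spelling as in the document) and withdrawal of consent or assent.
- **Section 4 (Trial Synopsis).** The corresponding entry is "Severe Adverse Event/Reaction", again beside withdrawal of assent or consent. It makes no link to praziquantel.

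Two other passages lean towards keeping children in follow-up. Section 8.4 states: "All participants will be enrolled for the duration of the 2-year follow-up post 1st treatment". On compliance, Section 11.1.1.10 states: "If the individual refuses treatment this will be entered into the treatment log". Neither deals with a child taken off praziquantel for safety.

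The primary outcome (8.6.1) is the 2-year ultrasound score and the secondary outcome (8.6.2) is the 2-year Kato-Katz count. Section 12.3.2 describes ultrasonography and stool collection as non-invasive.

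**The concern.** A child who must not take praziquantel again can still be scanned and can still give a stool sample. If the child instead leaves the trial, the primary and secondary outcomes are missing by rule. The comparison of arms as randomised then loses a child for a reason caused by treatment, and the number of occasions for that to happen rises with the number of doses.

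This belongs in the protocol and cannot be left to an analysis plan. An analysis plan can describe how missing outcomes are handled, but it cannot collect them. Nor can the site settle the matter case by case, because Section 23 rules out planned deviations and waivers. The text also leaves staff unsure what to do about a child with extensive rash or severe cramps: 10.5 lists that child for withdrawal, while Section 14 prescribes only referral and a visit.

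**Working it through.** **1. Which reactions trigger withdrawal, and from what**

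| Event | Section 14 | Section 10.5 | Synopsis |
|---|---|---|---|
| Facial oedema after a dose | Removed from the trial | Withdrawal criterion | Withdrawal criterion |
| Extensive urticarial rash or severe stomach cramps within 48 hours | Classed as a severe adverse reaction; referral and visit; silent on withdrawal | Withdrawal criterion, because it is a severe adverse reaction | Withdrawal criterion |
| Severe event not related to praziquantel | Not covered | Not covered | Covered on its literal wording |

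**2. Treatment stop or trial exit?** Section 14 is explicit that facial oedema ends trial participation. Section 10.5 does not state the consequence. Its heading concerns withdrawal of participants, and it lists the severe reaction beside withdrawal of consent, so trial exit is a natural reading but not the only one. Section 8.4 keeps all participants enrolled for two years. It is a general statement and does not override the specific rule in Section 14. No text available for this review says that a child taken off praziquantel keeps the 2-year ultrasound and Kato-Katz count.

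**3. Doses before the endpoint.** Section 11.1 gives totals of 3, 5 and 9 treatments, each including one final end-of-trial treatment. Section 12 places annual treatments after the scheduled assessments. Doses that can lead to withdrawal before the 2-year outcome:

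- control: 3 − 1 = 2
- 2x: 5 − 1 = 4
- 4x: 9 − 1 = 8

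The 4x arm therefore has four times as many occasions as control (8/2 = 4). This becomes a difference in losses only if the risk recurs with each dose. If the risk falls on the first dose alone, the arms do not differ.

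**4. Size under the facial-oedema rule.** The protocol gives no rate for facial oedema. The nearest entry in Section 11.1.1.8 is allergic reaction, listed as very rare, below 0.01%. Assume that facial oedema falls in that category, and take the category's upper limit as a per-dose risk, r = 0.0001. The proportion removed after k doses is 1 − (1 − r)^k:

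- control: 1 − 0.9999² = 0.02%, or 0.04 of a child per 200
- 2x: 1 − 0.9999⁴ = 0.04%, or 0.08 per 200
- 4x: 1 − 0.9999⁸ = 0.08%, or 0.16 per 200

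Over 600 children this is 0.04 + 0.08 + 0.16 = 0.28 of a child. For comparison, Section 17.2 already allows for 25% loss: 450/(1 − 0.25) = 600, so 150 children may be lost.

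**5. Size under the wider triggers.** No calculation is possible. Urticaria is listed at above 10%, but that entry is not limited to extensive rash. Abdominal pain is also listed at above 10%, with no separate figure for severe cramps. Any per-dose rate would be invented, and so would any bias or power loss derived from it.

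**The case against.** The strongest reply is that the passages conflict less than they seem to. Section 14 is an emergency procedure. It classes three reactions as severe and states one mandatory consequence for one of them. It does not say that a child with rash or cramps continues treatment, so it can be read alongside 10.5. Facial oedema also looks deliberately singled out, because a history of it after praziquantel is an exclusion criterion in 10.2. Both points stand, and a flat contradiction between 10.5 and Section 14 should not be claimed. They do not explain why follow-up should end: the exclusion criterion is a reason not to give the drug, not a reason to stop measuring.

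A reader might infer from the synopsis that any severe event, whatever its cause, removes a child, given that 13.4.3 defines severe as "Significant impairment of functioning; the subject is unable to carry out usual activities" or a risk to life. That reading rests on a terse synopsis entry, and the body section on withdrawal is specific to praziquantel. A wording slip is more likely than an intended rule.

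A reader might also infer that unequal withdrawal materially biases the 4x comparison or erodes power. The documents do not support this. They give no rate for the wider triggers. Section 6.2.2 associates the more severe reactions with longer and heavier dosing than the single doses of about 40 mg/kg used here. Section 17.4 plans sensitivity analyses for missing data.

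Finally, the Schedule of Assessments figure, the safety reporting flow chart and the consent pages were not available, so retention of such children could be stated there. That limits the claim of absence. It does not change what Section 14 says.

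**Conclusion.** The point holds as an inexpensive improvement. Section 14 expressly ends trial participation after facial oedema when stopping praziquantel would serve the safety purpose. Section 10.5, read the same way, extends this to every severe adverse reaction to praziquantel, and the synopsis is looser still. Outcomes that could be collected safely would then be given up, with more occasions for this where more doses are given.

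The expected loss under the facial-oedema rule is negligible, well under one child across the trial. That rests on treating the listed allergic-reaction frequency as a per-dose upper limit for facial oedema. Under the wider triggers the size is unknown, and it also depends on reading 10.5 as trial exit, which that section does not state. The 25% allowance and the planned sensitivity analyses limit the consequences but do not recover a measurable outcome. The case for change rests on an avoidable loss and unclear instructions to staff, not on any demonstrated effect on the primary result.

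**What to change.** - Align the synopsis with Section 10.5, so that the trigger is a severe adverse reaction to praziquantel.
- Make 10.5 and Section 14 agree on which reactions stop treatment. Whether extensive rash and severe cramps belong with facial oedema is for the clinical team to decide.
- In both sections, word the consequence as permanent discontinuation of praziquantel only.
- State that the child keeps the 2-year ultrasound and Kato-Katz count unless consent or assent is withdrawn.

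The cost is a short amendment. It needs sponsor agreement and REC approval (20.1, 20.3) and, judging by the amendment history in Appendix 3, NDA approval. The consent and assent wording may need checking, and any revised form would need REC approval and translation (12.2). In the field it means a few extra non-invasive assessments at a visit already scheduled.

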11.1 Treatment Summary

Praziquantel, ~40mg/kg, dependent on standardised and verified dose pole, which was developed by WHO in 2001 for the administration of praziquantel without the use of weighing scales (29,30). Maximum dose 4x600mg tablets. Total treatments detailed below include an end of trial final treatment.

Control arm: 3 treatments (1x per annum for 2-years + final treatment)
Intervention arm 1: 5 treatments (2x per annum for 2-years + final treatment)
Intervention arm 2: 9 treatments (4x per annum for 2-years + final treatment)

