12.3.2. Exploratory outcomes

Sample collections for the exploratory outcomes to be carried out where local conditions permit and involve:

Stool samples 4-week post-treatment egg reduction egg counts

Urine samples Pre-treatment and 4-week post-treatment CCA urinary

dip-stick diagnosis of *S. mansoni*. Parasites to be hatched

from stool samples for those positive by CCA.

Blood sample 8ml by phlebotomy for cellular and cytokine response

measurement.

ISRCTN Number: 16994599

All assessments are non-invasive (ultrasonography and stool collection), or considered of minor risk (phlebotomy).

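### A severe reaction to praziquantel takes the child out of the trial rather than off the drug, so the 2-year ultrasound is forfeited for a dose-related reason

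*Protocol*

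**What the plan says.** Three places in the protocol deal with a child who reacts badly to a dose.

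- Section 10.5, under participant withdrawal, lists "Severe Adverse Reaction to praziguantel" alongside withdrawal of consent or assent.
- The Trial Synopsis gives the criterion more loosely as "Severe Adverse Event/Reaction".
- Section 14 treats any of "facial oedema, an extensive urticarial rash or severe stomach cramps within the first 48-hours" after treatment as a severe adverse reaction, with referral to the health centre and a later home visit. It then adds, for one of the three signs only: "In the event of facial oedema as a result of treatment the child will be permanently removed from further participation in the trial".

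Section 11.1.1.9 gives dose modifications as not applicable. For a dose that is declined, 11.1.1.10 says "If the individual refuses treatment this will be entered into the treatment log", and nothing there ends participation. No matching route exists for a child whose doses are stopped because of a reaction.

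The primary outcome is the ultrasound pattern score at 2 years (8.6.1), and the secondary outcome is the egg count at the same time (8.6.2). Section 12.3.2 says of the procedures: "All assessments are non-invasive (ultrasonography and stool collection), or considered of minor risk (phlebotomy".

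**The concern.** Stopping a drug and leaving a trial are separate decisions, and these rules merge them. A child who should not receive more praziquantel can still be scanned and can still give a stool sample. A reaction to the drug is no stated reason to omit either. Section 23 also forbids planned deviations and waivers, so a site cannot arrange to scan a removed child as an exception. The text itself has to allow it.

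Dose frequency is what was randomised, and the removal trigger is tied to doses. Outcomes lost this way can therefore be lost in different proportions in the arms being compared. Section 17.4 promises to examine a range of missing-data assumptions, but it cannot recover an ultrasound that was never taken.

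A secondary point is which signs lead to removal. Section 10.5 combined with Section 14's definition points to withdrawal for all three. Section 14 states permanent removal for facial oedema alone. If that sentence is read as narrowing 10.5, a child with an extensive rash or severe cramps stays in and is dosed again.

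**Working it through.** **The plan's own figure.** Section 17.2 gives 92% power with 150 per arm, 80% versus 60%, at 1.66% (two-sided per 17.1). The normal approximation with pooled variance gives 92.2%, and 450 / (1 - 0.25) = 600. The design figures reproduce. The point below concerns who is measured, not the sample size.

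**Step 1. Doses before the primary assessment.** Section 11.1 gives totals of 3, 5 and 9; for the last it reads "Intervention arm 2: 9 treatments (4x per annum for 2-years + final treatment". Section 12 places annual treatment after the ultrasound, so the final dose follows the 2-year scan:

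- control: 3 - 1 = 2
- 2x arm: 5 - 1 = 4
- 4x arm: 9 - 1 = 8

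After a reaction to dose 1, there remain 1, 3 and 7 doses before the scan.

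**Step 2. How unequal the loss can be.** Let p be the per-dose risk of a reaction that leads to removal, equal across arms and constant over doses, with all scheduled doses given. The share removed before the scan is 1 - (1 - p)^k with k = 2, 4, 8.

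- 4x to 1x: [1 - (1 - p)^8] / [1 - (1 - p)^2]. This tends to 8/2 = 4 as p tends to 0; it is 3.97 at p = 0.25% and 3.77 at p = 2%.
- 2x to 1x: the limit is 4/2 = 2; it is 1.96 at p = 2%.
- If reactions occur only at the first dose, both ratios are 1.

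So the ratio lies between 1 and about 4 for the 4x arm, and between 1 and about 2 for the 2x arm, provided the risk does not rise over doses.

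**Step 3. Absolute size, for assumed rates.** The protocol lists urticaria and abdominal pains of any severity at over 10% (6.2.2, 11.1.1.8) but gives no rate for the extensive or severe forms. The values of p below are assumptions. Power takes these removals on top of the 25% allowance.

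| p per dose | % removed, 1x / 2x / 4x | Children of 200, 1x / 2x / 4x | Power, 4x vs 1x |
|---|---|---|---|
| 0.1% | 0.2 / 0.4 / 0.8 | 0.4 / 0.8 / 1.6 | 92.1% |
| 1% | 2.0 / 3.9 / 7.7 | 4.0 / 7.9 / 15.5 | 90.7% |
| 2% | 4.0 / 7.8 / 14.9 | 7.9 / 15.5 / 29.8 | 89.1% |

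**Step 4. If facial oedema alone leads to removal.** The protocol lists allergic reaction as very rare, below 0.01%. Assume that facial oedema falls under that heading and that the rate applies per dose. Doses before the scan are 200 x (2 + 4 + 8) = 2,800, so fewer than 2,800 x 0.0001 = 0.28 cases are expected in the whole trial. In the 4x arm the bound is 1,600 x 0.0001 = 0.16. This does not extend to rash or cramps.

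**Step 5. Effect on the estimate.** Take an intervention arm at the planned 60%, or 120 of 200, and lose 2 children (1%):

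- both without fibrosis: 120/198 = 60.6%, a shift of +0.6 points
- both with fibrosis: 118/198 = 59.6%, a shift of -0.4 points

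These are the extremes for a loss of that size.

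**The case against.** The strongest reply is that the dosing rule is already settled. Section 10.5 withdraws severe adverse reactions, and Section 14 defines all three signs as such. Its sentence on facial oedema can be read as stressing permanence for the one reaction that is also an exclusion criterion (10.2). That is the more natural reading, and it largely stands. A reader might infer that the protocol leaves re-dosing after rash or cramps wholly undecided; the documents do not support that. They contain one sentence that could be taken as an exception.

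A reader might also count two harms for a child with rash or cramps, further doses and a lost ultrasound. They are alternatives. If 10.5 governs, the child is withdrawn and there are no further doses. If Section 14 narrows it, the child stays in and is scanned.

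Nor does Section 8.4 contradict the removal rule. It says "All participants will be enrolled for the duration of the 2-year follow-up post 1st treatment", but that is a general statement of duration, and every withdrawal criterion is an exception to it.

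Finally, the effect may be negligible: 25% loss is already allowed for, and children with earlier facial oedema are excluded. This is fair as to size. It does not answer the main point, because neither the allowance nor the analysis in 17.4 collects the missing outcome.

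**Conclusion.** The point holds as a modest, avoidable weakness. As written, a child withdrawn for a severe reaction leaves the trial, and no section keeps that child for the 2-year ultrasound and egg count. The loss is triggered by doses, and planned doses before the assessment are 2, 4 and 8. It can therefore be unequal, by a factor of 1 to about 4 for the 4x arm against control, assuming the same per-dose risk in each arm that does not rise over doses.

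The number of children affected cannot be derived from the documents. It is very small if only facial oedema leads to removal, and larger if 10.5 is applied to all severe reactions. The likely effect on the estimate is small against a 20-point target. A reader might infer material bias in the primary comparison; nothing in the protocol supports that, since no rate for the severe forms is given. The case for change is that the loss serves no stated safety purpose and costs almost nothing to prevent.

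**What to change.** Use one rule in 10.5, Section 14 and the Trial Synopsis:

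1. Word the consequence as permanently stopping praziquantel, not as ending participation.
2. State which of the three signs trigger it. The sponsor chooses the clinical threshold: either all three, or facial oedema alone with an explicit decision on further dosing after rash or cramps.
3. Add: *Unless consent or assent is withdrawn, the child still has the 2-year ultrasound and egg count.*

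The cost is a wording amendment in three places. It needs sponsor agreement and REC approval (20.3) and probably NDA review, given how the amendment history describes earlier submissions. It would come mid-trial. No visit is added, because the ultrasound and stool sample are already scheduled at 2 years (12.5.2).
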